Subjects are numbered sequentially. Each subject screened (total of 25 screened) will be assigned a unique screening number for the duration of the study. Subject screening numbers will also become a subjects treatment number if they are enrolled in the study after providing informed consent and meeting inclusion criteria. Subjects who discontinue or withdraw from the study before receiving a treatment assignment code, but re-enroll at a later time must be assigned a new screening number. The investigator must maintain a master log linking the subject number to the subject's name. The investigator must follow all applicable privacy laws in order to protect a subject's privacy and confidentiality.

INVESTIGATIONAL DRUG SUPPLY :

Eligible participants will receive 900 mg intravenous spesolimab starting at Visit 2/week 0/Baseline. All participants will receive a total of 8 or 9 infusions (depending on dosing frequency) through Week 28 or Week 26 (depending on whether the subject's dosing frequency is increased to every 3 weeks at Week 8), unless there is significant worsening. All subjects should be observed for 30 minutes following the infusion at Baseline to assess safety. Select cases will be offered the opportunity to continue treatment through Week 52 on case-by-case basis if the patient would benefit from continued treatment. All subjects who have not been discontinued will be monitored once a month, for 4 months after treatment cessation.

All study medication will be provided by Boehringer Ingelheim, refrigerated and stored between 2-8°C in a secure area. Study drug will be administered to subjects at each study visit in office. The investigative site will account for all study drug dispensed and stored during the study.

STATISTICAL CONSIDERATIONS:

Sample Size

This is a proof-of-concept, open-label trial. Twenty patients will be enrolled in the trial to demonstrate efficacy of spesolimab in a population of patients with moderate-severe, refractory PG. Although there is no formal power calculation, a sample size of n=20 subjects allows 81% power at 2.5% significance for a one-sided binomial test to detect at Week 16 a difference of 36.6% in the proportion of GPG success compared to a constant set to be equal to 10%. The choice of the constant was based on data from a randomized clinical trial for efficacy of infliximab where a group of 17 PG placebo-treated patients showed 6% response at Week 2 (Brooklyn et al.,2006).

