Demographics and Other Baseline Characteristics

Descriptive statistics of demographics and other baseline characteristics of patients will be summarized with mean, median, and standard deviation for quantitative outcomes, and frequency and percentage tables for categorical outcomes.. Other baseline characteristics include sex, age, height, weight, vital signs, duration of PG, history of pathergy or PG trigger (if known), concurrent diagnoses from medical history and indications for concomitant medication, concomitant medication, and previous PG treatments.

Target Lesion Measurement and Digital Image Assessments

Size of target PG lesion will be approximated at each visit by measuring the length, width and depth of the lesion. Target lesion will also be analyzed using Image J software to obtain a more precise surface area of each lesion using digital photographs taken at each visit.

Analysis of Primary Endpoint

We will compare the proportion of patients achieving one-point decrease in target lesion GPG score at Week 16 with a constant p=0.10. Clopper-Pearson 90% confidence interval will be estimated.

Analysis of Secondary Endpoints

- One sided Clopper-Pearson 90% confidence intervals will be estimated for the proportion of patients achieving re-epithelization (GPG Severity Score of 0) at Visits 3, 4, 5, 6, 7, 8, and 9
- We will apply a two-sided paired t-test to evaluate significance of the mean difference of GPG score at Week 16 versus Week 0.
- Mean patient reported scores of pain (Pain VAS) and quality of life (DLQI) at baseline will be compared to those at Week 16 and treatment termination using the student's t- test to compare between subject's pre and post-treatment scores.
- One sided Clopper-Pearson 90% confidence intervals will be estimated for the proportion of patients with recurrence or worsening of PG lesions from point of complete re-epithelization or spesolimab cessation at end of treatment visit (Week 28 or Week 26 depending on dosing frequency).

Interim Analysis

An interim analysis will be performed after the first 10 subjects complete Week 16. We will continue enrollment during this time. Proportion of patients achieving one-point GPG score decrease will be reported. Changes from baseline at Week 16 in the PG lesions (number, size, GPG score) will be evaluated and reported. Enrolled subjects will continue to receive treatments during this time.

Data Transfer and Management

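### The primary analysis states only a 90% interval, which does not match the one-sided 2.5% test behind the sample size; at n=20 the two disagree at exactly 5 responders

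*Combined protocol and SAP*

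**What the plan says.** Under Statistical Considerations, the Sample Size paragraph gives n=20 as allowing "81% power at 2.5% significance for a one-sided binomial test", against a constant of 10%. The same paragraph says that this is not a formal power calculation.

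The Analysis of Primary Endpoint section reads: "We will compare the proportion of patients achieving one-point decrease in target lesion GPG score at Week 16 with a constant p=0.10". It then adds that a "Clopper-Pearson 90% confidence interval will be estimated". It gives no test, alpha or decision rule, and does not say whether the interval is one-sided or two-sided.

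The Analysis of Secondary Endpoints section does state sidedness. For healing: "One sided Clopper-Pearson 90% confidence intervals will be estimated for the proportion of patients achieving re-epithelization". For relapse: "One sided Clopper-Pearson 90% confidence intervals will be estimated for the proportion of patients with recurrence or worsening of PG lesions". Neither says whether the bound is a lower or an upper one.

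The Study Design Overview sets enrolment at up to 20 patients.

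**The concern.** A one-sided exact test at level alpha corresponds to a two-sided Clopper-Pearson interval at level 1 - 2 × alpha. A one-sided 2.5% test therefore goes with a two-sided 95% interval. A two-sided 90% interval goes with a one-sided 5% test, and a one-sided 90% bound with a one-sided 10% test. The plan uses one level to justify its size and another to report its main result, and does not explain the change.

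The interval is the only inferential tool that the primary analysis names, beside a comparison with 0.10, so readers will check whether it excludes 10%. For one realistic result, that check and the test in the Sample Size paragraph give opposite answers. With no rule fixed in advance, the reading of that result could be settled after the data are seen. The planned interim report of the responder proportion, after 10 subjects complete Week 16, is a reason to settle it early.

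The recurrence or worsening proportion has a smaller problem of the same kind. It is an unfavourable outcome, and an undirected one-sided bound does not say whether the reader will learn how high the rate could plausibly be.

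**Working it through.** **Inputs.** n=20, p0=0.10, one-sided alpha 0.025 and stated power 81% (Sample Size); 90% Clopper-Pearson interval (Analysis of Primary Endpoint). Assumptions: the binomial test is exact, and all 20 patients are analysed unless stated otherwise.

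**Step 1: the plan's own figure.** The cut is the smallest r with P(X ≥ r | 20, 0.10) ≤ 0.025.
- r=5: 0.0432, too large.
- r=6: 0.0113, so the cut is 6.

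Power is P(X ≥ 6 | 20, p1). At p1=0.366 it is 0.799, close to the stated 81%. The paragraph words 36.6% as a difference from 10%; taken literally, p1=0.466 and power is 0.959. The stated power therefore fits 36.6% as the response rate, and power below is quoted on that reading.

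**Step 2: test and interval side by side.** For x responders out of n, the Clopper-Pearson lower limit is the a-quantile of Beta(x, n-x+1) and the upper limit is the (1-a)-quantile of Beta(x+1, n-x). Here a=0.05 for two-sided 90%, 0.10 for one-sided 90% and 0.025 for two-sided 95%.

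| Responders | One-sided p against 0.10 | Two-sided 90% | One-sided 90% lower limit | Two-sided 95% |
|---|---|---|---|---|
| 4/20 | 0.133 | 7.1% to 40.1% | 9.0% | 5.7% to 43.7% |
| 5/20 | 0.0432 | 10.4% to 45.6% | 12.7% | 8.7% to 49.1% |
| 6/20 | 0.0113 | 14.0% to 50.8% | 16.6% | 11.9% to 54.3% |

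At 4/20 the test fails and every interval includes 10%. At 6/20 the test succeeds and every interval excludes it. At 5/20 the test fails, yet both 90% versions exclude 10%; the 95% interval includes it, in line with the test.

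**Step 3: error rates of the two readings.** If the true rate is 10%:
- cut of 6 (2.5% test): type I error 0.0113;
- cut of 5 (90% lower limit above 10%): type I error 0.0432.

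The difference, 0.0432 - 0.0113 = 0.0319, is the probability of exactly 5/20.

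**Step 4: how likely the disputed result is.** P(X=5 | 20, p) is 3.2% at p=0.10, 20.2% at 0.25, 10.9% at 0.366 and 2.8% at 0.466.

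**Step 5: fewer than 20 analysed.** Smallest number of responders that excludes 10%:

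| n | One-sided 2.5% test | Two-sided 90% interval | One-sided 90% bound |
|---|---|---|---|
| 20 | 6 | 5 | 5 |
| 19 | 6 | 5 | 5 |
| 18 | 6 | 5 | 4 |
| 17, 16, 15 | 5 | 5 | 4 |
| 14 | 5 | 4 | 4 |

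With a two-sided 90% interval the conflict disappears at n=15 to 17. With a one-sided bound it remains at every n shown.

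**Step 6: direction of the recurrence bound.** Illustration only, with an assumed 2 recurrences among 10 patients: the one-sided 90% lower bound is 5.5% and the upper bound is 45.0%. Only the upper bound shows how much recurrence the data still allow.

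**The case against.** The strongest reply is that the plan does not contain two success thresholds. A reader might infer that 5/20 is a declared success by the interval and a declared failure by the test. The documents do not support that: the interval is only to be estimated, and no sentence makes a lower limit above 10% the criterion. An interval may be reported for precision at a level other than the test's. The 2.5% test itself appears only in a paragraph that disclaims a formal power calculation. This objection stands against the stronger reading. It leaves the narrower point, because the primary analysis names a comparison with 0.10 and gives the reader nothing but a 90% interval with which to make it.

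It can also be said that this is a small, open-label proof-of-concept trial, that one outcome is affected at n=20, that even the looser reading has a type I error below 5%, and that anyone can recompute an interval from the responder count. All of this is true and limits the severity. Against it, the Sample Size paragraph states its purpose plainly: "Twenty patients will be enrolled in the trial to demonstrate efficacy of spesolimab".

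A reader might further infer that 90% is wrong for the secondary proportions. The documents do not support that either: no null value or test is attached to them, so a 90% level contradicts nothing, and asking for 95% throughout would be a preference. Only the missing direction of the bound needs attention, chiefly for recurrence or worsening.

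**Conclusion.** The concern holds as a mismatch of levels plus a missing decision rule; it should be fixed, but it is not critical. With 20 analysed and an exact test, the two readings part only at 5/20: p=0.043 against a threshold of 0.025, while the 90% lower limit is 10.4% (two-sided) or 12.7% (one-sided). The implied type I error is 4.3% instead of 1.1%.

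This rests on the interval being read against 10%, which the plan invites but does not prescribe. It does not depend on the interval's sidedness at n=20. It does depend on the number analysed: under a two-sided interval there is no conflict at n=15 to 17.

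**What to change.** In the Analysis of Primary Endpoint section, name the exact one-sided binomial test at 2.5% against 0.10 and report a two-sided 95% Clopper-Pearson interval. Define success as p ≤ 0.025, equivalently a 95% lower limit above 10%, for the number actually analysed. That means at least 6 responders if n=20; a fixed cut of 6 should not be written in, because the cut is 5 at n=15 to 17. This keeps the design as sized, with power 79.9% if the response rate is 36.6%.

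If the sponsor prefers the two-sided 90% interval, that is equally coherent, provided the Sample Size paragraph is restated as a one-sided 5% test: cut 5/20, exact alpha 4.3%, power about 91% if the response rate is 36.6%.

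For the recurrence or worsening proportion, report an upper bound or a two-sided interval.

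The cost is a few sentences of wording, best settled before the interim report. The 95% interval is slightly wider: at 5/20 it runs from 8.7% to 49.1% instead of 10.4% to 45.6%. Sample size, visits and data collection do not change.

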ENDPOINTS:

Primary Endpoint

- One point decrease from baseline in target lesion Global PG (GPG) Severity Score at Week 16

Secondary Endpoints

- Complete re-epithelization of PG lesions (GPG Severity Score of 0) at visits 3, 4, 5, 6, 7, 8, and 9.
- Absolute change from baseline in patient-reported pain severity (Pain-VAS) at visits 3, 4, 5, 6, 7, 8, and 9 and at complete re-epithelization of ulcer.
- Absolute change in quality of life (DLQI) from baseline at visits 3, 4, 5, 6, 7, 8, and 9 and at complete re-epithelization of ulcer.
- Recurrence of PG lesions after complete re-epithelization (GPG score 0) of all lesions and spesolimab cessation

- Time to worsening (1 or more GPG point increase) of target PG lesion from spesolimab cessation

STUDY DESIGN OVERVIEW:

This study is a prospective, proof-of-concept, open label clinical trial. The study will take place at Icahn School of Medicine at Mount Sinai.

The study will screen up to 25 subjects in order to enroll a total of up to 20 patients with at least one clinically measurable ulcerative PG lesion. Subjects will receive 900 mg of spesolimab intravenously (IV) over 90 minutes at a frequency of every 4 weeks until Week 28 with the following exceptions:

- At the Week 8 visit, subjects who do not show any improvement, show only minimal improvement, or those that begin to lose their initial improvement response (decrease in pain or wound drainage), may be switched to a dosing frequency of every 3 weeks through Week 26, at the discretion of the investigator. These subjects will still return at Week 16 for an endpoint visit, but will not receive treatment at this visit. Refer to Tables 3 and 4 for schedule of events.

All subjects will be monitored monthly for 4 months subsequent to treatment cessation.

Subjects who reach GPG score 0 at anytime during the study will continue to receive treatments until week 28 (or Week 26 depending on dosing frequency) and will then be monitored for 4 months subsequent to treatment cessation.

Subjects who are experiencing improvement in their PG but who have not reached complete wound healing will continue treatment until Week 28 (or Week 26 for those who were switched to every 3 week dosing), even if primary endpoint has been achieved. These subjects will then be monitored for 4 months subsequent to treatment cessation.

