- Urine pregnancy test for all female subjects of child-bearing potential to confirm subject is not pregnant
- Collect blood samples for CBC with differential, CMP, and C-reactive protein (CRP), serum cytokine profiling (O-link® inflammatory cytokine panel, IL-1 β , and IL-36 subtypes), Nab, ADA, and Pre- and post dose pharmacokinetics.
- Administer study drug

Spesolimab Treatment Phase

Visits 3 thru 9 (subjects that dose every 4 weeks) or Visits 3 thru 11 (subjects that are switched to every 3 week dosing at Week 8)

- Record concomitant medications (including use of pain medication) and adverse events
- Urine pregnancy test for all female subjects of child-bearing potential to confirm subject is not pregnant
- Patient Pyoderma Gangrenosum Questionnaires and DLQI
- Obtain vital signs
- Standardized clinical photography of target lesion and other PG lesions
- PG clinical assessments (including number/location/measurements of PG lesions and GPG score for target lesion)
- Assess status of associated comorbid conditions (improved, no change, worse)
- Collect blood samples for CBC with differential, CMP, and C-reactive protein (CRP)
- **Only at Week 8 and Week 28 (subjects dosed every 4 weeks) or Week 26 (subjects switched to dosing every 3 weeks):** Nab, ADA, and pre dose pharmacokinetics.
- **Only at Week 16:** serum cytokine profiling (O-link® inflammatory cytokine panel, IL-1 β , and IL-36 subtypes), Nab, ADA, and pre dose pharmacokinetics.
- Administer study drug

Post-Spesolimab Follow-up Phase

Visits 10 thru 13 (subjects dosed every 4 weeks) or Visits 12-15 (subjects switched to dosing every 3 weeks)

Follow-Up Visits at 1 Month, 2 Months, 3 Months and 4 Months Post-Spesolimab Treatment Cessation

- Record concomitant medications (including use of pain medication) and adverse events
- Patient Pyoderma Gangrenosum Questionnaires and DLQI
- Assess status of associated comorbid conditions (improved, same, worse)
- Standardized clinical photography of target lesion and other PG lesions

- PG clinical assessments (including number/location/measurements of PG lesions, and GPG score of target lesion)
- Collect blood for serum cytokine profiling (O-link® inflammatory cytokine panel, IL-1 β , and IL-36 subtypes)
- If subject worsens or sees progression of their PG during the 4- month follow-up period (defined as 1 or more increase in GPG score of target lesion), then patient will be discontinued from the study and started on available, standard PG therapies.

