Visit #	1	2	3	4	5	6	7	8	9	10	11	12	13		
Visit Type	Screening	Baseline	TX	TX	TX	TX	TX	TX	TX	F/Up	F/Up	F/Up	F/Up	Early Term (ET)	Additional Treatment Visits
Standardized Photographs		X	X	X	X	X	X	X	X	X	X	X	X	X	X
Record and changes related to associated conditions (such as IBD, RA, etc) if applicable		X	X	X	X	X	X	X	X	X	X	X	X	X	
Serum Cytokine Profile O-Link Inflammatory Panel		X				X				X	X	X	X	X	
Pharmacokinetics, ADA, NAb		X		X		X			X					X	
Dispense Drug		X	X	X	X	X	X	X	X						
Concomitant Medications	X ⁴	X	X	X	X	X	X	X	X	X	X	X	X	X	X
Adverse Events	X	X	X	X	X	X	X	X	X	X	X	X	X	X	X

¹ Includes current and past medical conditions in addition to personal and family history of inflammatory bowel disease, rheumatoid arthritis, and autoimmune conditions as well as history of myeloproliferative disorders and malignancy

² Includes height and weight (only at screening), blood pressure, and pulse

³ Pre-dose PK, ADA, NAb samples will be obtained at selected visits (Visit 2, 4, 6, and 9 or ET). At Week 0/Visit 2, a post-dose PK samples will also be obtained approximately 5 mins after end of i.v. infusion.

⁴ Record all concomitant medications at each visit, and at screening also collect any medications taken within the last 30 days, and previous therapies/treatments for PG (including systemic and topical treatments, and invasive treatment such as surgery, radiation and cryotherapy).

Table 4. Schedule of Events Q4 Week Dosing through Week 8 Followed by Q3 Week Dosing Through Week 26

Visit Week	(Up to -28 Days before Baseline)	0	4	8	11	14	16	17	20	23	26	4 wk post-spesolimab last dose	8 wk post-spesolimab last dose	12 wk post-spesolimab last dose	16 wk post-spesolimab last dose		
Visit #	1	2	3	4	5	6	7	8	9	10	11	12	13	14	15		
Visit Type	Screening	Baseline	TX	TX	TX	TX		TX	TX	TX	TX	F/Up	F/Up	F/Up	F/Up	Early Term (ET)	Additional Treatment Visits
Informed Consent	X																
Inclusion/Exclusion Criteria	X	X															
Demographics/Medical Hx ¹	X																
Limited Physical Exam	X	X															
Vitals ²	X	X	X	X	X	X	X	X	X	X	X					X	X
Serum Preg Test	X																
Urine Preg Test		X	X	X	X	X	X	X	X	X	X					X	X
CBC w/differential, CMP and CRP	X	X	X	X	X	X	X	X	X	X	X					X	X
Screening for TB (Quantiferon Gold, or PPD), HIV, HepB and HepC	X																
PG Clinical Assessments (including number, location and measurements)	X	X	X	X	X	X	X	X	X	X	X	X	X	X	X	X	X
Global PG (GPG) Severity Score	X	X	X	X	X	X	X	X	X	X	X	X	X	X	X	X	X

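### Re-epithelization rates are indexed by visit number, but Visits 5 to 9 fall at different weeks in the two dosing schedules, so each rate mixes time points up to 8 weeks apart

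*Combined protocol and SAP*

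**What the plan says.** The Secondary Endpoints list names "Complete re-epithelization of PG lesions (GPG Severity Score of 0) at visits 3, 4, 5, 6, 7, 8, and 9". The Analysis of Secondary Endpoints repeats the list, with a one-sided 90% Clopper-Pearson interval "for the proportion of patients achieving re-epithelization (GPG Severity Score of 0) at Visits 3, 4, 5, 6, 7, 8, and 9". Neither place separates the two schedules or says how their visit numbers correspond.

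There are two schedules. Table 3 covers dosing every four weeks through Week 28. The other is "Table 4. Schedule of Events Q4 Week Dosing through Week 8 Followed by Q3 Week Dosing Through Week 26". The Procedures section gives the treatment phase as Visits 3 to 9 for the first group and "Visits 3 thru 11 (subjects that are switched to every 3 week dosing at Week 8") for the second. According to the Study Design Overview, the switch is open at Week 8, at the investigator's discretion, to subjects with no improvement, minimal improvement or a fading response.

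Pain and quality of life are also defined by visit number: "Absolute change from baseline in patient-reported pain severity (Pain-VAS) at visits 3, 4, 5, 6, 7, 8, and 9" and "Absolute change in quality of life (DLQI) from baseline at visits 3, 4, 5, 6, 7, 8, and 9", each with a further time point at complete healing. Their analysis is set differently: mean scores "at baseline will be compared to those at Week 16 and treatment termination".

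**The concern.** A rate labelled Visit 7, 8 or 9 should describe patients at one point in time. Here it would combine four-week subjects with switched subjects seen 4, 7 or 8 weeks earlier. Switched subjects are selected for poor response, so the slower healers would be assessed at the earlier time. Their assessments at Weeks 23 and 26, including their end of treatment, would not count in any re-epithelization rate.

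Complete healing is the first secondary endpoint listed. From Visit 5 on, its by-visit results could not be labelled with a week. If the choice between visit and week is left until the data are in hand, it becomes a post-hoc choice in an open-label trial.

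**Working it through.** **Inputs.** The week of each visit comes from the header rows of Tables 3 and 4. The infusion totals come from Investigational Drug Supply. The absence of a Week 16 infusion for switched subjects comes from the Study Design Overview.

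**Check of the mapping against the plan's own figure.** Table 3 doses at Visits 2 to 9: 9 − 2 + 1 = 8 infusions. Table 4 has Visits 2 to 11, which is 10 visits; less the undosed Week 16 visit, that is 9 infusions. Both agree with the stated 8 or 9. (The drug row of Table 4 does carry a mark at Week 16, which would make 10. That row and the text must be reconciled, but the assessment weeks used here do not depend on it.)

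**Gap at each visit number.** Gap = Table 3 week − Table 4 week. Prior infusions are those given before the visit, taking Week 16 as undosed for switched subjects.

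| Visit | Table 3 week | Table 4 week | Gap (weeks) | Prior infusions, Table 3 / Table 4 |
|---|---|---|---|---|
| 3 | 4 | 4 | 0 | 1 / 1 |
| 4 | 8 | 8 | 0 | 2 / 2 |
| 5 | 12 | 11 | 1 | 3 / 3 |
| 6 | 16 | 14 | 2 | 4 / 4 |
| 7 | 20 | 16 | 4 | 5 / 5 |
| 8 | 24 | 17 | 7 | 6 / 5 |
| 9 | 28 | 20 | 8 | 7 / 6 |

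Three things follow:

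- At Visit 9, switched subjects are 26 − 20 = 6 weeks before their last scheduled dose.
- Week 16 is Visit 6 in Table 3 and Visit 7 in Table 4, so no visit-indexed rate describes Week 16 for everyone.
- Switched Visits 10 and 11 (Weeks 23 and 26) lie outside the list, although GPG is scored at both. That is 2 unused assessments per switched subject for re-epithelization only. If 8 of 20 switch (an assumption; range 4 to 12), it is 16 (8 to 24).

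**Possible size at Visit 9.** This is an illustration; the healing curve and the number switched are not in the documents. Assume a constant healing hazard, equal in both schedules, with a proportion P healed by Week 28. Then λ = −ln(1 − P)/28 and F(t) = 1 − exp(−λt). With k of 20 switched:

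- Rate at Visit 9 = [(20 − k)·F(28) + k·F(20)]/20
- Rate at end of treatment = [(20 − k)·F(28) + k·F(26)]/20
- Shortfall = (k/20)·[F(26) − F(20)]

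For P = 40%, λ = 0.01824, F(20) = 30.6% and F(26) = 37.8%.

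- k = 5: 37.6% at Visit 9 against 39.4% at end of treatment, a shortfall of 1.8 points.
- k = 10: 35.3% against 38.9%, a shortfall of 3.6 points.

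Over P from 30% to 60% and k of 5 or 10, the shortfall runs from 1.4 points (P = 30%, k = 5) to 4.6 points (P = 60%, k = 10). One patient in 20 is 5 points.

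**Indexing by week instead.** Weeks 4, 8, 16 and 20 match exactly (switched Visits 3, 4, 7 and 9). Week 12 pairs with 11, 24 with 23, and 28 with 26. The gaps become 0, 0, 1, 0, 0, 1 and 2 weeks.

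**Pain and DLQI.** The definitions call for change at seven visits and at complete healing. The analysis gives two times, Week 16 and treatment termination. Both times exist in both schedules, so the planned tests are not misaligned; it is the definitions that carry the visit-number problem. The other times defined have no stated analysis.

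**The case against.** Much of the plan is already set by week. The primary endpoint and the GPG mean comparison use Week 16, which both schedules visit. Pain and DLQI use Week 16 and treatment termination. The recurrence analysis names Week 28 or Week 26 according to dosing frequency. All of this stands: a reader might infer that the secondary analyses in general run by visit number, but in the analysis section only re-epithelization does. For the same reason, Visit 11 of switched subjects is not lost to the trial; as their end of treatment it serves the pain, DLQI and recurrence analyses.

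Visit number is not arbitrary either. Prior infusions are equal through Visit 7 and differ by one at Visits 8 and 9, so visits roughly index dose number. That softens the point about exposure but not the one about time, and the plan does not offer dose number as its reason.

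Nor does the plan say in words that the schedules are combined. That is inferred from one proportion per visit with no split, which is what an analyst following the text would produce.

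The affected intervals have no null value or decision rule, the illustrated shift is under one patient in 20 and understates healing, and rates by week remain recoverable from the data collected. These points lower the severity; they do not remove the defect.

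A reader might also infer that pain and DLQI will be compared with an unpaired test, because the word paired appears for GPG but not for them. The text does not support this. It describes comparing subjects' scores before and after treatment, the endpoint is change from baseline, and a paired test is a Student's t-test. Only a word is missing.

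**Conclusion.** The re-epithelization analysis is wrong as written and should be fixed before analysis. The gaps of 1, 2, 4, 7 and 8 weeks at Visits 5 to 9, and the omission of switched subjects' Visits 10 and 11 from the rates, follow directly from the two schedule tables and need no assumption beyond reading the plan as one proportion per visit. Because switching depends on response at Week 8, the mixing is not random.

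The numerical effect is uncertain and probably modest. The 1.4 to 4.6 points at Visit 9 rest on a constant, equal healing hazard, 30% to 60% healed by Week 28, and 5 or 10 of 20 switched. Slower healing in switched subjects, or a benefit from more frequent dosing, would change it.

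For pain and DLQI the fault is a mismatch between definition and analysis, not a misaligned test. The primary endpoint is not touched, so this is a point to correct rather than a threat to the trial's main conclusion.

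**What to change.** In Secondary Endpoints and in Analysis of Secondary Endpoints, replace Visits 3 to 9 with Weeks 4, 8, 12 (11 if switched), 16, 20, 24 (23 if switched) and scheduled end of treatment (28, or 26 if switched). State that each rate includes both schedules under this pairing.

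Use the same weeks for change from baseline in pain and DLQI, so that definition and analysis agree, and add the word paired to their t-test as a clarification. A repeated-measures model over these weeks is an option, not a requirement.

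The cost is endpoint and SAP wording plus a few lines of code, with no new visits or data. There is one small loss. Switched subjects' Weeks 14 and 17 (Visits 6 and 8) have no four-week counterpart, so they leave the by-week rates and should be listed descriptively. Each switched subject still contributes seven assessments, as now (Visits 3, 4, 5, 7, 9, 10 and 11 in place of 3 to 9). The gain is therefore alignment and an end-of-treatment rate, not more data.
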